1 PROTOCOL SYNOPSIS

PROTOCOL TITLE																	
Phase I-II study to assess venetoclax + azacitidine and donor lymphocyte infusion in patients with MDS or AML (with marrow blasts < 30%) in relapse after allogeneic hematopoietic stem cell transplantation (VENTOGRAFT study)																	
STUDY DRUGS	Venetoclax																
EudraCT NUMBER	2021-000632-56																
Number of Patients	Approximately 48 adult patients will be enrolled into the study																
Study Population	Adult patients with MDS or AML with less than 30% blasts in relapse after Allo-SCT																
STUDY PHASE	I/II																
Study Sites	Approximately 20 sites																
Inclusion Criteria																	
Patients must meet all of the following inclusion criteria to be eligible for enrollment into the study:																	

 1. Documented relapse of MDS or AML with marrow blasts < 30% (with WBC < 15000/mm³) after allo-SCT. 2. Age ≥ 18 years. 3. Eastern Cooperative Oncology Group (ECOG) performance status ≤ 2. 4. Patient must have adequate organ function as indicated by the following laboratory values: 																	

  
 System	Laboratory Value	
   
 Renal	
 
 Serum creatinine	< 2 mg/dl	
 
 or calculated creatinine clearance^a	OR ≥ 30 mL/min for patients with creatinine levels > 1.5 x institutional ULN	
 
 Hepatic	
 
 Serum total bilirubin	≤ 2.5 x ULN OR direct bilirubin ≤ ULN for patients with total bilirubin levels ≥ 2 mg/dL.	
 
 AST (SGOT) and ALT (SGPT)	≤ 2.5 x ULN	
 
 Alkaline Phosphatase	≤ 5 x ULN	
  
		System	Laboratory Value	Renal		Serum creatinine	< 2 mg/dl	or calculated creatinine clearance ^a	OR ≥ 30 mL/min for patients with creatinine levels > 1.5 x institutional ULN	Hepatic		Serum total bilirubin	≤ 2.5 x ULN OR direct bilirubin ≤ ULN for patients with total bilirubin levels ≥ 2 mg/dL.	AST (SGOT) and ALT (SGPT)	≤ 2.5 x ULN	Alkaline Phosphatase	≤ 5 x ULN
System	Laboratory Value																
Renal																	
Serum creatinine	< 2 mg/dl																
or calculated creatinine clearance ^a	OR ≥ 30 mL/min for patients with creatinine levels > 1.5 x institutional ULN																
Hepatic																	
Serum total bilirubin	≤ 2.5 x ULN OR direct bilirubin ≤ ULN for patients with total bilirubin levels ≥ 2 mg/dL.																
AST (SGOT) and ALT (SGPT)	≤ 2.5 x ULN																
Alkaline Phosphatase	≤ 5 x ULN																

	If > 2.5 x ULN, then liver fraction should be ≤ 2.5 x ULN
^a Creatinine clearance should be calculated per institutional standard.	

5. Patient not refractory to platelet transfusions.6. Female subject of childbearing potential must practice at least one protocol specified method of birth control (see Appendix 3), starting on Study Day 1 through at least 30 days after the last dose of venetoclax or 3 months after the last dose of azacitidine. Not being of childbearing potential is defined as:
- Age > 55 years with no menses for 12 or more months without an alternative medical cause, or- Age ≤ 55 years with no menses for 12 or more months without an alternative medical cause AND an FSH level > 40 IU/L, or- Permanent surgical sterility (bilateral oophorectomy, bilateral salpingectomy or hysterectomy).7. Female subjects of childbearing potential must have negative results for pregnancy test performed:
- At Screening with a serum sample obtained within 14 days prior to the first study drug administration, and- Prior to dosing with urine sample obtained on Cycle 1 Day 1, if it has been > 7 days since obtaining the serum pregnancy test results.Female subjects who are not of childbearing potential at Screening do not require pregnancy testing.8. Male subjects sexually active with female partner(s) of childbearing potential, must agree from first dose of study drug(s) through at least 30 days after the last dose of venetoclax or 3 months after the last dose of azacitidine, whichever is later, to practice the protocol specified contraception (see Appendix 3).9. Patient is available for periodic blood sampling, study related assessments, and appropriate clinical management at the treating institution for the duration of the study.10. Patient has the ability to understand and willingness to sign an informed consent form indicating the investigational nature of the study.11. Patient is able to swallow capsules.	
Exclusion Criteria	
Patients with any one of the exclusion criteria listed below are not eligible for the study:	

1. Patient has active and uncontrolled infection.2. Patient has active acute or chronic GVHD.3. Patient receives more than 1mg/kg/day prednisolone.4. Patient has uncontrolled intercurrent illness or circumstances that could limit compliance with the study, including but not limited to the following: symptomatic	

- congestive heart failure, unstable angina pectoris, uncontrolled cardiac arrhythmia, pancreatitis, or psychiatric or social conditions that may interfere with patient compliance.
5. Patient is currently participating or has participated in a study with an investigational compound or device within 30 days of initial dosing with study drug.
 6. Patient has known human immunodeficiency virus (HIV) infection or HIV-related malignancy.
 7. Patient has clinically active hepatitis B or hepatitis C infection.
 8. Patient has a known allergy or hypersensitivity to any component of VENETOCLAX or AZA.
 9. Patient with a "currently active" second malignancy, other than non-melanoma skin cancer and carcinoma in situ of the cervix, should not be enrolled. Patients are not considered to have a "currently active" malignancy if they have completed therapy for a prior malignancy, are disease free from prior malignancies for > 5 years or are considered by their physician to be at less than 30% risk of relapse.
 10. Patient has received growth factors such as erythropoietin alfa (EPO) or granulocyte colony-stimulating factor (G-CSF) or has received non cytotoxic agents (including low dose oral chemotherapy) in the 30 days before inclusion. In case of previous cytotoxic treatment, an interval of 3 months is required.
 11. Patient is on any systemic steroids that have not been stabilized to the equivalent of ≤ 10 mg/day prednisone during the 4 weeks prior to the start of the study drugs.
 12. Patients with clinical evidence of CNS leukemia.
 13. Patient has a history of GI surgery or other procedures that might interfere with the absorption or swallowing of the study drugs.
 14. Subject enrolled in a Dose-Escalation cohort has received strong or moderate CYP3A inhibitors (**see appendix 2 for examples**) within 3 days prior to the first dose of study drug.
 15. Patient is unable to take and/or tolerate oral medications on a continuous basis.
 16. Patient is pregnant or breastfeeding within the projected duration of the study.
 17. Subject has a malabsorption syndrome or other condition that precludes an enteral route of administration.
 18. Absence of social security.

STUDY OBJECTIVES

Objectives

The objectives of this study are to assess the safety, and efficacy, of venetoclax in combination with AZA/DLI in patients with MDS and AML with marrow blasts < 30% (myeloid neoplasms) in relapse after allogeneic hematopoietic stem cell transplantation.

Phase I:

- Assess the safety profile of venetoclax in combination with AZA/DLI

- Determine the recommended Phase II dose (RPTD)

Phase II: Determine the efficacy of venetoclax in combination with AZA/DLI

STUDY ENDPOINTS

Primary endpoint:

Phase I: To determine toxicity profile and safety of the combination

Phase II: Overall hematological response rate of venetoclax in combination with AZA/DLI

Response assessment will be performed for MDS according to modified IWG 2006 criteria and according to European LeukemiaNet criteria for AML.

Secondary endpoints:

- ✓ Toxicity as measured by NCI CTCAE 5.0
- ✓ Acute and chronic GVHD rate
- ✓ Duration of response (DOR)
- ✓ Overall survival (OS)
- ✓ Progression-free survival (PFS)
- ✓ Event-free survival (EFS)

Exploratory endpoint:

- ✓ Study the correlation between patient overall mutational status before treatment and response
- ✓ The prognostic impact of MRD on outcome

STUDY DESIGN

This is an open label multicenter phase I/II study. Patients will be treated with venetoclax during 14 days in combination with AZA at 75 mg/m²/day for 5 days for each cycle or 50 mg/m²/day for 5 days each cycle if relapse occurred less than 4 months after allo SCT.

Patients who meet eligibility criteria will be administered VENETOCLAX orally at starting dose in phase I part and at MTD in phase II part on days 1-14 in combination with AZA at 75 mg/m²/day for 5 days for each cycle (on days 1-5) or 50 mg/m²/day for 5 days each cycle if relapse occurred less than 4 months after allo SCT.

Following cycles must be administered on day 28 or delayed until day 42 in cases of hematological toxicity. Each cycle will last 28 days starting on day 1 of each cycle when ANC > 1 G/L and platelet > 50 G/L without transfusion or when recovery of baseline level.

In the phase I part, VENETOCLAX will be given once daily orally on days 1-14 for all cycles at escalating doses starting at Dose Level 1 (defined below) in combination with AZA +/- DLI. Patients will receive at least 8 cycles of VENETOCLAX/AZA/DLI unless progression occurs. Response will be assessed after 4, 6 and 8 cycles. Patients achieving a response (defined below) will be able to continue on protocol with VENETOCLAX + AZA until 12 cycles maximum then with AZA alone. In the absence of response, patients will stop treatment.

Dose Levels for Treatment in Phase I

Dose Level	VENETOCLAX (mg)	Azacitidine (mg/m ²)
-1	50 mg*	75 (50 if relapse < 4 months)
1 (Starting dose)	100 mg*	75 (50 if relapse < 4 months)
2	200 mg*	75 (50 if relapse < 4 months)
3	400 mg*	75 (50 if relapse < 4 months)

*VENETOCLAX will be given once daily orally during 14 days.

In the phase II part, VENETOCLAX will be given once daily orally on days 1-14 for all cycles at MTD defined in the phase I part of the study in combination with AZA/DLI. Patients will receive at least 8 cycles of VENETOCLAX/AZA/DLI unless progression occurs. Response will be assessed after 4, 6 and 8 cycles. Patients achieving a response (defined below) will be able to continue on protocol with VENETOCLAX + AZA until 12 cycles maximum then AZA alone. In the absence of response, patients will stop treatment.

Ramp-up** will be performed at the beginning of cycle 1 :

Dose Level	VENETOCLAX D1C1	VENETOCLAX D2C1	VENETOCLAX D3C1 and beyond
-1	10 mg*	20 mg*	50 mg*
1 (Starting dose)	20 mg*	50 mg*	100 mg*
2	50 mg*	100 mg*	200 mg*
3	100 mg*	200 mg*	400 mg*

*VENETOCLAX will be given once daily orally

**Therapy with CYP3A inhibitor are not allowed during the ramp up.

DLI will be infused every two cycles (C2, C4, C6, C8) at day 15 in absence of GVHD as follows, and at least 8 weeks after immunosuppressive therapy discontinuation. If the chimerism in > 90% recipient, DLI will not be performed.

	DLI dosage
Sibling-Id or Unrelated Donor-Id 10/10	0.5 x 10 ⁷ CD3/kg 1 x 10 ⁷ CD3/kg 0.5 x 10 ⁸ CD3/kg 1 x 10 ⁸ CD3/kg
Unrelated Donor-Id 9/10	1 x 10 ⁶ CD3/kg 5 x 10 ⁶ CD3/kg 1 x 10 ⁷ CD3/kg 0.5 x 10 ⁸ CD3/kg

INVESTIGATIONAL PRODUCT

Venetoclax

Venetoclax will be administered at dose levels defined for the cohort a given subject is assigned to at Screening.

Each dose of venetoclax should be taken with approximately 240 mL of water within 30 minutes after the completion of a meal (preferably breakfast). Exceptions may apply if food is not allowed for medical procedures. Tablets must be swallowed whole and must not be broken, chewed, or crushed. The dose should be administered at the same time each day.

On days of concomitant administration of azacitidine, venetoclax should be given prior to azacitidine.

If vomiting occurs after taking venetoclax, do not take any additional dose that day. Take the next dose at the usual time the next day. A missed dose of venetoclax should be taken with food and water within 8 hours of the missed dose. After 8 hours, the missed dose should not be taken. The next dose of venetoclax will be the regularly scheduled dose.

Azacitidine

Azacitidine will be administered at the dose of 75 mg/m²/day for 5 days for each cycle or 50 mg/m²/day for 5 days each cycle if relapse occurred less than 4 months after allo SCT and should be prepared according to the information provided in the Summary of Product Characteristics (SmPC) and will be administered, by IV infusion or SC injection.

BIOLOGICAL STUDIES

Mutational analysis (Hematology Laboratory, CHRU Lille)

Immunologic analysis (Immunology Laboratory, Saint Louis hospital, Paris and INSERM U1065, Mediterranean center of molecular medicine, Nice)

At screening and during follow up (after 4 and 8 cycles and at the end of the study) presence of all identified mutations will be investigated with the same technique. All mutation-specific primers and probes will be designed by Biorad (Hercules, CA).

OVERALL DURATION OF THE STUDY: 42 MONTHS

Recruitment months: 24 months

Duration of Treatment: 12 months

Follow-up for all patients: 6 months

2 SUMMARY OF RATIONALE

a) MDS and AML in relapse after allo hematopoietic stem cell transplantation and their current treatment
Among patients with acute myeloid leukemia (AML), allogeneic hematopoietic stem cell transplantation (allo-HSCT) used as post-remission therapy for those with high-risk molecular profiles or as salvage therapy for those with resistant disease offers the highest potential for long-term survival[1]. In addition, allo-HSCT is the only curative option for patients with myelodysplastic syndromes (MDS) and chronic myelomonocytic leukemia (CMML)[2]. Still, relapse after allo-HSCT remains the major cause of treatment failure and is associated with a dismal prognosis[3]. Treatment options for those patients are mainly restricted to chemotherapy, donor lymphocyte infusions (DLI) or second allo-HSCT [4]. Treatment approach should ideally offer efficient antileukemic activity, acceptable toxicity and mechanisms to direct the donor immune system towards an enhanced graft-versus-leukemia effect without provoking graft-versus-host disease (GvHD). To fulfil all criteria, combination of azacitidine (AZA) to donor lymphocyte infusion (DLI) could be used in patients with relapse inferior to 2 years after allo-HSCT. AZA is approved for the treatment of patients with high-risk MDS and AML [5, 6]. Beyond its direct cytotoxic effects and ability to induce remissions even in patients refractory to chemotherapy, AZA is considered to increase the immunogenicity of AML blasts by re-expression of important antigens[7-9]. Furthermore, animal models suggest an immunomodulatory role of AZA that might attenuate GvHD after DLI [10, 11]. Combination was evaluated in AZARELA trial [12]. Treatment schedule contained up to eight AZA cycles (100 mg/m²/day, days 1–5, every 28 days) followed by DLI (from 1–5 x 10⁶ to 1–5 x 10⁸ CD3 cells/kg) after every second AZA cycle. A median of three courses AZA (range 1–8) were administered and 22 patients (73%) received DLI. Overall response rate was 30%, including seven complete remissions (CR, 23%) and two partial remissions (7%)[12, 13]. Incidence of acute and chronic

graft-versus-host disease was 37% and 17%, respectively. Azacitidine and DLI as salvage therapy is safe, induces long-term remission and is today a standard of care for patients in relapse after allo-HSCT [14].

b) VENETOCLAX

VENETOCLAX/GDC-0199 is a selective inhibitor of B-cell lymphoma-2 (BCL-2). The BCL-2 gene prevents apoptosis of some cells, including lymphocytes and can be highly expressed in cancers in the lymph nodes, spleen and other organs of the immune system. VENETOCLAX is designed to block the function of the BCL-2 protein by restoring the communication system that tells cancer cells to self-destruct. VENETOCLAX is approved for the treatment of patients with chronic lymphocytic leukemia (CLL), and is in clinical trials for small lymphocytic lymphoma (SLL), non-Hodgkin's lymphoma, multiple myeloma and acute myelogenous leukemia (AML). The effects of VENETOCLAX in combination with AZA in patients with MDS and AML have been reported in phase I. Ten patients received AZA + VENETOCLAX with VENETOCLAX at 400 mg (Cohort 1, n=4) and 800 mg (Cohort 2, n=6). Treatment-emergent adverse events (AEs) were febrile neutropenia, constipation, cough, nausea. The most common grade 4 AEs were a decrease in platelet count (30%), neutrophil count (20%), and white blood cell count (20%). The most frequent serious AE was febrile neutropenia (30%). Overall response rate was 70% (7/10 pts). Mutational profile of these patients weren't available[15]. Phase III is ongoing in patients ineligible for intensive chemotherapy.

c) Use of DLI and AZA + DLI in France

In 2018, french guidelines about use of donor lymphocyte infusion were published by Francophone Bone Marrow Transplantation and Cellular Therapy (SFGTM-TC)[16]. Donor lymphocyte infusion (DLI) can be proposed to treat or prevent the relapse of malignant hemopathies following allogeneic stem cell transplantation. Doses of DLI were defined in the guidelines and were commonly used in all French centers. Response rate of DLI in AML or MDS patients were around 20-40% alone[17]. Response rate is higher in defavorable cytogenetic AML patients[18]. A german retrospective study has evaluated combination of azacitidine and donor lymphocyte infusions following relapse after allogeneic hematopoietic stem cell transplantation in AML and MDS [19]. Combination AZA + DLI showed an overall response rate of 33% including 27% and 6% of complete and partial remission, respectively. Based on these results, using of AZA + DLI in combination is the classical regimen used today in France at relapse. During the 8 past years, 64/475 (13%) DLI including 53% in combination with AZA were performed in France based from SFGM-TC data in relapsed MDS/AML.

d) Rationale for the combination of AZA + DLI and VENETOCLAX

In the present study, we will use the combination of these two drugs to try to create a synergetic effect and generate a response for patients in relapse after allo-HSCT. The rationale of combining AZA + VENETOCLAX + DLI is to increase anti leukemic effect before DLI. It was shown that the response rate after DLI is higher in low disease AML patients[18]. Moreover, VENETOCLAX was shown to induce a switch between naive and memory B-cell subsets with 80% VENETOCLAX dose-dependent decrease of autoreactive B cells in autoimmune disease like lupus. In parallel, there were no consistent or marked changes in neutrophils, natural killer cells, hemoglobin, or platelets[20]. Hypothesis will be that AZA + VENETOCLAX could induce more GvL with low GHD rate. We will begin by VENETOCLAX as single agent during 28 days before starting the combination with AZA to reduce potential hematological side effects especially in this population after allo-SCT. Overexpression of BCL-2 has been implicated in the maintenance and survival of AML cells and

associated to resistance to chemotherapy. As BCL-2 has been observed to be up-regulated in AML patients [21, 22] and blocks differentiation of myeloid progenitors, it may be considered as a potential candidate progression gene of MDS transformation. The primary antiapoptotic mechanism of BCL-2 action is interaction with proapoptotic members of the BCL-2 family to block the mitochondrial permeability transition and release of cytochrome C[23]. Bogenberger et al. showed the in vitro role of VENETOCLAX in combination with azacitidine in AML, myelodysplastic syndrome (MDS) and chronic myelomonocytic leukemia (CMML)[24]. Therefore, use of VENETOCLAX could be a good therapeutic strategy in MDS and AML.

3 HYPOTHESIS

Based on AZARELA trial results, we assume that approximately 30% of responses due to AZA/DLI effects only might be observed. The objective is to demonstrate a 20% increase in response due to the addition of VENETOCLAX (i.e. from 30% to 50% after 6 cycles of AZA/DLI + VENETOCLAX). For the phase I, a design "3+3" will be used including between 9 to 18 patients. For the phase II, a two-stage design will be used. Under $H_0=30\%$ and $p_1=50\%$, the study with $\alpha=0.05$ and $\beta=0.2$, if 3 responses or less are observed in the first 14 evaluable patients, there will be no further inclusions (the inclusions would be terminated early), but all patients on treatment and that continue to derive clinical benefit according to the opinion of the investigator while tolerating study-treatment may continue to receive treatment according to the protocol.

If 4 or more responses are observed, 16 additional patients will be included in the study. If 13 responses or more are observed in evaluable patients, further investigation is warranted to compare AZA/DLI and combination of AZA/DLI and VENETOCLAX. We consider that a maximum of 10% of the population may not be evaluable for response and that a total of 48 patients will be needed to address the question.

All patients on treatment and that continue to derive clinical benefit according to the opinion of the investigator while tolerating study-treatment may continue to receive treatment at the cohort-assigned dose level.

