For the phase II, a two-stage design will be used. With the assumption that the AZA/DLI gives 30 % of ORR, with the assumption that AZA/DLI + VENETOCLAX gives 50 % of ORR, and with an alpha risk of 0.05 and a beta risk of 80% with a drop-out of 10%, to confirm the safety and evaluate efficacy, for the phase II, 30 patients should be treated at the optimal dose (27 patients + drop-out of 10%).

Overall, a maximum of 48 patients will be treated: 9 - 18 in phase I and 30 in phase II.

Statistical analysis plan

Analysis will be based on an intent-to-treat basis, whether or not the patient receives the protocol treatment.

It will be performed once the sample size has been reached in each group, separately.

It will be based on the computation of response rate, with 95% confidence interval.

Randomization / Stratification

Not applicable for this trial.

Methods of Statistical analysis

A summary of the planned statistical analyses are described. Structured analyses will be specified in a separate statistical analysis plan (SAP) prior to the end of the data management process and before receiving final study data. If analyses should be conducted deviating from the following descriptions, these deviations also will be specified in the SAP prior to receiving final study data.

Descriptive Statistics

For continuous variables mean, standard deviation (SD), median, interquartile range, minimum and maximum will be presented.

For categorical variables absolute and relative frequencies will be presented.

Interim analysis

An interim analysis is planned during the phase II to evaluate the effectiveness of treatment.

If 3 responses or less are observed in the first 14 evaluable patients, there will be no further inclusions (the inclusions would be terminated early), but all patients on treatment and that continue to derive clinical benefit according to the opinion of the investigator while tolerating study-treatment may continue to receive treatment according to the protocol.

If 4 or more responses are observed, 16 additional patients will be included in the study.

Final analysis

The final report of the study and the compilation of the statistical report will be performed within 12 months after completion and correction of all case report forms (database lock).

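### The phase II two-stage rule does not deliver the stated alpha of 0.05 together with 80% power at any evaluable number from 27 to 30, and the denominator for the final cut-off is not fixed

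*Protocol*

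**What the plan says.** Section 3 (Hypothesis) takes the null from an earlier trial of azacitidine plus donor lymphocytes: "we assume that approximately 30% of responses due to AZA/DLI effects only might be observed". The target is a rise "from 30% to 50% after 6 cycles of AZA/DLI + VENETOCLAX". The section sets alpha at 0.05 and beta at 0.2 and then gives the rule. Stage 1: "if 3 responses or less are observed in the first 14 evaluable patients, there will be no further inclusions". Stage 2: "If 4 or more responses are observed, 16 additional patients will be included in the study" (section 10.2, with the same rule in section 3). Final decision: "If 13 responses or more are observed in evaluable patients, further investigation is warranted". Section 3 also allows for up to 10% of patients not being evaluable for response.

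Section 10.2 (Sample size calculation) repeats the hypotheses "with an alpha risk of 0.05 and a beta risk of 80% with a drop-out of 10" per cent. It sets phase II at 30 treated patients, explained as 27 plus a 10% drop-out allowance. Its overall maximum of 48 is 18 in phase I plus 30 in phase II. The same section puts all included patients in the full analysis set and calls the analysis intent-to-treat.

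Neither section says whether alpha is one- or two-sided, and neither prints a denominator beside the cut-off of 13.

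**The concern.** Hypotheses, stage sizes, boundaries and error rates are all fixed in the protocol, so the error rates can be checked against the rule. Read plainly, with 14 + 16 = 30 evaluable patients, the rule has the stated power but an alpha well above 0.05. Read with the 27 evaluable patients of section 10.2, it has an acceptable alpha but power far below 80%.

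This rule is the trial's efficacy decision and the trigger for a comparative study. If venetoclax adds nothing and all 30 patients are evaluable, the chance of a false go is about 1 in 12 (0.083), where the protocol implies 1 in 20. If only 27 are evaluable and the combination does reach 50%, the chance of missing it is about 35% (1 - 0.65), where the protocol implies 20%. Without a fixed denominator, nobody can say which of these applies.

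**Working it through.** **Inputs.** p0 = 0.30, p1 = 0.50, alpha = 0.05, beta = 0.2, n1 = 14, stop at 3 or fewer, 16 added, success at 13 or more (section 3); 27 patients plus 10% drop-out = 30 (section 10.2). Assumption: alpha is one-sided in the upper tail, because the stated aim is an increase ("The objective is to demonstrate a 20% increase in response due to the addition of VENETOCLAX") and success is a minimum count.

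**Formula.** With n evaluable patients in total,

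P(success | p) = sum over x = 4 to 14 of P(Bin(14, p) = x) × P(Bin(n - 14, p) ≥ 13 - x).

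Alpha is this at p = 0.30, power at p = 0.50.

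**The plan's own figures.** The drop-out step reproduces: 27 / 0.90 = 30. At n = 30 the power is 0.8135, so the stated 80% reproduces too. Alpha does not. Its terms at p = 0.30, n = 30 are:

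| x in first 14 | P(x) | P(enough in next 16) | product |
|---|---|---|---|
| 4 | 0.2290 | 0.0257 | 0.0059 |
| 5 | 0.1963 | 0.0744 | 0.0146 |
| 6 | 0.1262 | 0.1753 | 0.0221 |
| 7 | 0.0618 | 0.3402 | 0.0210 |
| 8 | 0.0232 | 0.5501 | 0.0128 |
| 9 | 0.0066 | 0.7541 | 0.0050 |
| 10 | 0.0014 | 0.9006 | 0.0013 |
| 11 or more | 0.0002 | about 1 | 0.0002 |
| **sum** | | | **0.0829** |

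The futility stop is not the cause: a single-stage rule of at least 13 of 30 has alpha 0.0845.

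**Other evaluable counts, cut-off held at 13.**

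| evaluable n | one-sided alpha | power |
|---|---|---|
| 30 | 0.083 | 0.81 |
| 29 | 0.064 | 0.77 |
| 28 | 0.049 | 0.71 |
| 27 | 0.036 | 0.65 |

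No row has alpha at or below 0.05 with power of 0.80.

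**Cut-off moved to 14 of 30.** Alpha 0.0397, power 0.7051.

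**Could other boundaries rescue 30 patients?** No. A full search of two-stage designs for 0.30 against 0.50 finds none with alpha ≤ 0.05 and power ≥ 0.80 below 39 patients. At 39, stopping at 6 or fewer of 19 and requiring at least 17 of 39 gives 0.0455 and 0.804.

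**All 30 included patients as denominator, non-evaluable counted as non-responders.** If 10% are non-evaluable at random in both stages, the effective rates are 0.9 × 0.30 = 0.27 and 0.9 × 0.50 = 0.45. The same formula with n = 30 and cut-off 13 gives 0.039 and 0.63. With cut-off 14, power is 0.495. Under this convention the alpha computed with no losses is an upper bound.

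**The case against.** The strongest reply is that 0.083 is only the case with no losses. The cut-off applies to evaluable patients, 10% may not be evaluable, and section 10.2 itself works from 27. At 28 evaluable patients alpha is 0.049, and at 27 it is 0.036. If the first 14 are evaluable by definition and each of the 16 added patients has a 10% chance of not being so, the averages are alpha 0.057 and power 0.73. This stands as a limit on the finding: a reader might infer that the type I error simply is 0.083, with power met and alpha missed, and the document does not support that as a fixed statement. It does not rescue the plan, because every count that brings alpha to 0.05 or below takes power to 0.71 or lower.

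A reader might also argue that at 13 of 30 the exact 95% interval is 25.5% to 62.6% and includes 30%, so a declared success would contradict the planned analysis. The protocol plans a binomial interval as a summary and does not tie the decision to it, and a two-sided interval need not agree with a one-sided rule. That comparison is illustrative only.

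The rule is also only a single-arm screen: success leads to further investigation, not to a confirmatory claim. That makes a higher alpha defensible if it is stated openly. It does not make the printed 0.05 correct. The beta of 80% in section 10.2 is clearly a slip for power, since section 3 has beta 0.2.

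**Conclusion.** The stated pair, alpha 0.05 with beta 0.2, is wrong for the printed rule at every evaluable count from 27 to 30. One-sided alpha runs from 0.083 down to 0.036, while power runs from 0.81 down to 0.65. Thirty is the most natural denominator, because 14 + 16 = 30 and it alone reproduces 80% power, but the protocol does not print it and section 10.2 points to 27.

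The result assumes exact binomial sampling and a one-sided alpha. If alpha were two-sided, leaving 0.025 in the upper tail, the shortfall at 30 would be larger (0.083), and even 27 would miss (0.036). The protocol does not settle which was meant.

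The 39-patient result shows that the stated pair is out of reach with 30. It does not follow that the trial must be enlarged, because a screening study may use other error rates if it states them.

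**What to change.** Amend sections 3 and 10.2 before any phase II data are seen. The timing matters because 13 of 30 is a success under one option below and a failure under the other.

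1. **Fix the denominator.** Print it beside the final cut-off and reconcile 14 + 16 = 30 with 27 plus drop-out. One way that fits the intent-to-treat and full-analysis-set text is to use all 30 included patients, with non-evaluable patients counted as non-responders, and to apply the same convention at stage 1.
2. **Restate the operating characteristics for that denominator.** Either keep at least 13 of 30 and print one-sided alpha 0.083 and power 0.81, or use at least 14 of 30 and print alpha 0.040 and power 0.705. In either case note that these powers assume no non-evaluable patients. With 10% counted as non-responders, power for 13 of 30 is about 0.63.
3. **Correct the wording.** Say that alpha is one-sided, and replace the beta of 80% with power 80% (beta 20%) or with the restated power.

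The cost is protocol wording in two sections and one less favourable printed figure. No patients are added.
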